2.5 Baseline Evaluation

Screening evaluations performed within 8 weeks prior and within 10 days prior to treatment initiation will be used as baseline.

3 STUDY IMPLEMENTATION

3.1 Study Design

This will be an open label study in which all patients receive pembrolizumab. Patients will be assigned to specific cohorts based on their previous treatment with an immune stimulating therapeutic cancer vaccine.

Treatment Duration with Pembrolizumab: 2 years (at 3 week intervals)

3.2 Trial Treatments

The treatment to be used in this trial is outlined below in **Table 3**

Table 3 Trial Treatment

Drug	Dose/Potency	Dose Frequency	Route of Administration	Regimen/Treatment Period	Use
Pembrolizumab	200 mg	Q3W	IV infusion	Day 1 of each 3 week cycle	Experimental
Treatment Duration with Pembrolizumab: 2 years (3 week intervals)					

Trial treatment should begin on the day of enrollment or as close as possible to that date.

3.3 Drug Administration

Trial treatment should be administered on Day 1 of each cycle after all procedures/assessments have been completed as detailed on the Study Calendar (Section 3.4). Trial treatment may be administered up to 7 days before or after the scheduled Day 1 of each cycle due to administrative reasons.

All trial treatments will be administered on an outpatient basis.

Pembrolizumab 200 mg will be administered as a 30 minute IV infusion every 3 weeks. Every effort should be made to target infusion timing to be as close to 30 minutes as possible.

However, a window of -5 minutes and +10 minutes is permitted (i.e., infusion time is 30 minutes: -5 min/+10 min). Premedication for patients who experience an infusion reaction should be administered 60 minutes (+/- 30 minutes) prior to the infusion.

The Pharmacy Manual contains specific instructions for the preparation of the pembrolizumab infusion fluid and administration of infusion solution. Pembrolizumab is administered through a 0.2 to 5 micron sterile, nonpyrogenic, low-protein binding inline or add-on filter. Do not infuse other medications through the same infusion line.

3.3.1 Dose Modifications

Adverse events (both non-serious and serious) associated with pembrolizumab exposure may represent an immunologic etiology. These adverse events may occur shortly after the first dose or several months after the last dose of treatment. Pembrolizumab must be withheld for drug-related toxicities and severe or life-threatening AEs as per **Table 4** below. See Section 4 for supportive care guidelines, including use of corticosteroids.

Table 4. Dose Modification Guidelines for Drug-Related Adverse Events

Toxicity	Hold Treatment For Grade	Timing for Restarting Treatment	Treatment Discontinuation
Diarrhea/Colitis	2-3	Toxicity resolves to Grade 0-1	Toxicity does not resolve within 12 weeks of last dose or inability to reduce corticosteroid to 10 mg or less of prednisone or equivalent per day within 12 weeks
	4	Permanently discontinue	Permanently discontinue
AST, ALT, or Increased Bilirubin	2	Toxicity resolves to Grade 0-1	Toxicity does not resolve within 12 weeks of last dose
	3-4	Permanently discontinue (see exception below) ^a	Permanently discontinue
Type 1 diabetes mellitus (if new onset) or Hyperglycemia	T1DM or 3-4	Hold pembrolizumab for new onset Type 1 diabetes mellitus or Grade 3-4 hyperglycemia associated with evidence of beta cell failure	Resume pembrolizumab when patients are clinically and metabolically stable
Hypophysitis	2-4	Toxicity resolves to Grade 0-1. Therapy with pembrolizumab can be continued while endocrine replacement therapy is instituted	Toxicity does not resolve within 12 weeks of last dose or inability to reduce corticosteroid to 10 mg or less of prednisone or equivalent per day within 12 weeks

Toxicity	Hold Treatment For Grade	Timing for Restarting Treatment	Treatment Discontinuation
Hyperthyroidism	3	Toxicity resolves to Grade 0-1	Toxicity does not resolve within 12 weeks of last dose or inability to reduce corticosteroid to 10 mg or less of prednisone or equivalent per day within 12 weeks
	4	Permanently discontinue	Permanently discontinue
Hypothyroidism		Therapy with pembrolizumab can be continued while thyroid replacement therapy is instituted	Therapy with pembrolizumab can be continued while thyroid replacement therapy is instituted
Infusion Reaction	2 ^b	Toxicity resolves to Grade 0-1	Permanently discontinue if toxicity develops despite adequate premedication
	3-4	Permanently discontinue	Permanently discontinue
Pneumonitis	2	Toxicity resolves to Grade 0-1	Toxicity does not resolve within 12 weeks of last dose or inability to reduce corticosteroid to 10 mg or less of prednisone or equivalent per day within 12 weeks
	3-4	Permanently discontinue	Permanently discontinue
Renal Failure or Nephritis	2	Toxicity resolves to Grade 0-1	Toxicity does not resolve within 12 weeks of last dose or inability to reduce corticosteroid to 10 mg or less of prednisone or equivalent per day within 12 weeks
	3-4	Permanently discontinue	Permanently discontinue
All Other Drug-Related Toxicity ^c	3 or Severe	Toxicity resolves to Grade 0-1	Toxicity does not resolve within 12 weeks of last dose or inability to reduce corticosteroid to 10 mg or less of prednisone or equivalent per day within 12 weeks
	4	Permanently discontinue	Permanently discontinue

Note: Permanently discontinue for any severe or Grade 3 drug-related AE that recurs or any life-threatening event.

^a For patients with liver metastasis who begin treatment with Grade 2 AST or ALT, if AST or ALT increases by greater than or equal to 50% relative to baseline and lasts for at least 1 week then patients should be discontinued.

^b If symptoms resolve within one hour of stopping drug infusion, the infusion may be restarted at 50% of the original infusion rate (e.g., from 100 mL/hr to 50 mL/hr). Otherwise dosing will be held until symptoms resolve and the subject should be premedicated for the next scheduled dose; Refer to **Table 5** – Infusion Reaction Treatment Guidelines for further management details.

^c Patients with intolerable or persistent Grade 2 drug-related AE may hold study medication at physician discretion. Permanently discontinue study drug for persistent Grade 2 adverse reactions for which treatment with study drug has been held, that do not recover to Grade 0-1 within 12 weeks of the last dose.

Dosing interruptions are permitted in the case of medical / surgical events or logistical reasons not related to study therapy (e.g., elective surgery, unrelated medical events, patient vacation, and/or holidays). Subjects should be placed back on study therapy within 6 weeks of the

Abbreviated Title: Pembrolizumab in MTC

Version Date: 3/26/18

scheduled interruption. The reason for interruption should be documented in the patient's study record.

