3.5.1 Criteria for removal from protocol therapy

- Completion of protocol therapy
- Clinical progression of disease based on increased symptoms or immune related response criteria (irRC) to also be implemented for disease progression as described in 6.3.2.
- Grade 3 or greater toxicity attributed to treatment that does not resolve to grade 1 within 21 days from time of scheduled treatment.
- Grade 3 or greater autoimmune disease that threatens vital organs.
- Intercurrent illness or medical circumstances. If at any time the constraints of this protocol are detrimental to the patient's health, the patient may be removed from protocol therapy and reasons for withdrawal will be documented.
- Subject decides to withdraw from the study (In this event, the reasons for withdrawal will be documented)
- Investigator discretion
- Positive pregnancy test

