11.1.2 Toxicity

- Immune-mediated pneumonitis, including fatal cases, occurred in patients receiving pembrolizumab. Pneumonitis occurred in 32 (2.0%) of 1567 patients, including Grade 1 (0.8%), 2 (0.8%), and 3 (0.4%) pneumonitis. Monitor patients for signs and symptoms of pneumonitis. Evaluate suspected pneumonitis with radiographic imaging. Administer corticosteroids for Grade 2 or greater pneumonitis. Withhold pembrolizumab for Grade 2; permanently discontinue pembrolizumab for Grade 3 or 4 or recurrent Grade 2 pneumonitis.
- Immune-mediated colitis occurred in 31 (2%) of 1567 patients, including Grade 2 (0.5%), 3 (1.1%), and 4 (0.1%) colitis. Monitor patients for signs and symptoms of colitis. Administer corticosteroids for Grade 2 or greater colitis. Withhold pembrolizumab for Grade 2 or 3; permanently discontinue pembrolizumab for Grade 4 colitis.
- Immune-mediated hepatitis occurred in 16 (1%) of 1567 patients, including Grade 2 (0.1%), 3 (0.7%), and 4 (0.1%) hepatitis. Monitor patients for changes in liver function. Administer corticosteroids for Grade 2 or greater hepatitis and, based on severity of liver enzyme elevations, withhold or discontinue pembrolizumab.
- Hypophysitis occurred in 13 (0.8%) of 1567 patients, including Grade 2 (0.3%), 3 (0.3%), and 4 (0.1%) hypophysitis. Monitor patients for signs and symptoms of hypophysitis (including hypopituitarism and adrenal insufficiency). Administer corticosteroids and hormone replacement as clinically indicated. Withhold pembrolizumab for Grade 2; withhold or discontinue for Grade 3 or 4 hypophysitis.
- Hyperthyroidism occurred in 51 (3.3%) of 1567 patients, including Grade 2 (0.6%) and 3 (0.1%) hyperthyroidism. Hypothyroidism occurred in 127 (8.1%) of 1567 patients, including Grade 3 (0.1%) hypothyroidism. Thyroid disorders can occur at any time during treatment. Monitor patients for changes in thyroid function (at the start of treatment, periodically during treatment, and as indicated based on clinical evaluation) and for clinical signs and symptoms of thyroid disorders. Administer replacement hormones for hypothyroidism and manage hyperthyroidism with thionamides and beta-blockers as appropriate. Withhold or discontinue pembrolizumab[®] (pembrolizumab) for Grade 3 or 4 hyperthyroidism.

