- Type 1 diabetes mellitus, including diabetic ketoacidosis, occurred in 3 (0.1%) of 2117 patients. Monitor patients for hyperglycemia or other signs and symptoms of diabetes. Administer insulin for type 1 diabetes, and withhold pembrolizumab and administer anti-hyperglycemics in patients with severe hyperglycemia.
- Immune-mediated nephritis occurred in 7 (0.4%) of 1567 patients, including Grade 2 (0.2%), 3 (0.2%), and 4 (0.1%) nephritis. Monitor patients for changes in renal function. Administer corticosteroids for Grade 2 or greater nephritis. Withhold pembrolizumab for Grade 2; permanently discontinue pembrolizumab for Grade 3 or 4 nephritis.
- Other clinically important immune-mediated adverse reactions can occur. For suspected immune-mediated adverse reactions, ensure adequate evaluation to confirm etiology or exclude other causes. Based on the severity of the adverse reaction, withhold

pembrolizumab and administer corticosteroids. Upon improvement to Grade 1 or less, initiate corticosteroid taper and continue to taper over at least 1 month. Based on limited data from clinical studies in patients whose immune-related adverse reactions could not be controlled with corticosteroid use, administration of other systemic immunosuppressants can be considered. Resume pembrolizumab when the adverse reaction remains at Grade 1 or less following corticosteroid taper. Permanently discontinue pembrolizumab for any Grade 3 immune-mediated adverse reaction that recurs and for any life-threatening immune-mediated adverse reaction.

- The following clinically significant, immune-mediated adverse reactions occurred in less than 1% (unless otherwise indicated) of 1567 patients: arthritis (1.6%), exfoliative dermatitis, bullous pemphigoid, uveitis, myositis, Guillain-Barré syndrome, myasthenia gravis, vasculitis, pancreatitis, hemolytic anemia, and partial seizures arising in a patient with inflammatory foci in brain parenchyma.
- Severe and life-threatening infusion-related reactions have been reported in 3 (0.1%) of 2117 patients. Monitor patients for signs and symptoms of infusion-related reactions including rigors, chills, wheezing, pruritus, flushing, rash, hypotension, hypoxemia, and fever. For Grade 3 or 4 reactions, stop infusion and permanently discontinue pembrolizumab.

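### Table 4 allows pembrolizumab to restart after a second Grade 2 pneumonitis that resolves in time; Section 11.1.2 requires a permanent stop

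*Combined protocol and SAP*

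**What the plan says.** Section 3.3.1 makes Table 4 the dosing rule: "Pembrolizumab must be withheld for drug-related toxicities and severe or life-threatening AEs as per" that table. The pneumonitis row has two lines.

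- **Grade 2:** hold, then restart once the event is back to Grade 0-1. Discontinue if "Toxicity does not resolve within 12 weeks of last dose or inability to reduce corticosteroid to 10 mg or less of prednisone or equivalent"; the steroid limit is a daily dose, to be reached in the same 12-week window.
- **Grade 3-4:** permanently discontinue.

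Neither line distinguishes a first episode from a later one. The note under the table does address recurrence, but only at higher severity: "Permanently discontinue for any severe or Grade 3 drug-related AE that recurs or any life-threatening event".

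Section 11.1.2 gives its own instruction for pneumonitis: "permanently discontinue pembrolizumab for Grade 3 or 4 or recurrent Grade 2 pneumonitis". It also gives the background rate: "Pneumonitis occurred in 32 (2.0%) of 1567 patients, including Grade 1 (0.8%), 2 (0.8%), and 3 (0.4%) pneumonitis".

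**The concern.** The two sections lead to different actions for one identifiable patient: someone with a second Grade 2 pneumonitis that returns to Grade 0-1 within 12 weeks, with the steroid down to 10 mg or less of prednisone equivalent per day. Table 4 lets that patient be treated again. Section 11.1.2 does not.

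The more permissive text is the one that will be used. Section 3.3.1 points to Table 4, and the supportive care guidance in 4.1.3 sends the reader back to 3.3.1 for dose modification. Section 10.4 cites Section 11 only for the side effect profile. A clinician who follows those directions need never meet the stricter rule.

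What is at stake is patient safety. Section 11.1.2 reports that immune-mediated pneumonitis has included fatal cases, although it gives no outcomes for recurrent Grade 2 events specifically. The participants have few or no symptoms, and Section 10.5 says that such patients are usually just monitored and that benefit in this disease is not yet established. That favours the stricter rule.

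**Working it through.** **Comparison of the rules.** Each provision that might apply is tested on the patient described above.

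| Provision | What it covers | Result for this patient |
|---|---|---|
| Table 4, pneumonitis Grade 2 | Restart at Grade 0-1; stop for non-resolution or failed taper | Restart allowed |
| Table 4, pneumonitis Grade 3-4 | Permanent stop | Does not apply |
| Table 4 note | Recurrence of severe or Grade 3 events; life-threatening events | Does not apply |
| Table 4 footnote c | Grade 2 events that persist; attached to the row for all other toxicities | Does not apply |
| 3.5.1, toxicity and autoimmune bullets | Both start at Grade 3 | Do not apply |
| 3.5.1, investigator discretion and medical circumstances | Removal is permitted | Stop possible, not required |
| 4.1.3, pneumonitis Grade 2 | Steroids and taper | No rule on recurrence |
| 11.1.2, pneumonitis | Recurrent Grade 2 | Permanent stop required |

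The wording of three of these matters. Footnote c reads "Permanently discontinue study drug for persistent Grade 2 adverse reactions for which treatment with study drug has been held", so it concerns persistence, not recurrence. The first toxicity bullet in 3.5.1 is "Grade 3 or greater toxicity attributed to treatment that does not resolve to grade 1 within 21 days from time of scheduled treatment", which cannot reach a Grade 2 event. The Table 4 note matches the general recurrence rule in 11.1.2, "Permanently discontinue pembrolizumab for any Grade 3 immune-mediated adverse reaction that recurs". The general rule was therefore carried into Table 4, and the pneumonitis-specific rule was not.

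**How often it could arise.** The protocol states no figure for this, so there is none to reproduce.

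Inputs from the documents:
- Grade 2 pneumonitis rate: 0.008 (Section 11.1.2)
- Accrual ceiling: 32 patients (Section 8)

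Assumed, because the documents give no value:
- Recurrence probability r: 0.10, 0.25 or 0.50
- Share of first cases that restart, and share of recurrences that are Grade 2 and resolve in time: both 1 for an upper bound, both 0.5 for a lower scenario

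First Grade 2 cases:
- Expected number: 32 × 0.008 = 0.256
- Chance of at least one: 1 − (1 − 0.008)^32 = 0.227

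For affected patients, the upper bound on the expected number is 32 × 0.008 × r, and the upper bound on the chance of at least one is 1 − (1 − 0.008r)^32. The lower scenario multiplies the per-patient probability by 0.5 × 0.5 = 0.25, giving 1 − (1 − 0.008 × r × 0.25)^32.

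| r (assumed) | Expected, upper bound | Chance of at least one, upper bound | Chance of at least one, lower scenario |
|---|---|---|---|
| 0.10 | 0.026 | 0.025 | 0.0064 |
| 0.25 | 0.064 | 0.062 | 0.0159 |
| 0.50 | 0.128 | 0.120 | 0.0315 |

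**The case against.** The strongest reply is that both texts can be obeyed. Table 4 is titled as guidelines, and its restart column sets a condition for resuming without ordering it. The mandatory wording in 3.3.1 concerns withholding. A clinician who stops after a second Grade 2 episode breaks nothing in Table 4, so 11.1.2 could be read as filling a gap in a summary table. On that reading the stop rule already exists and only a cross-reference is missing.

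Part of this stands. Table 4 does not mention a second episode; the restart follows from a Grade 2 line with no limit on recurrence. But the possibility of obeying both does not help a clinician who is directed only to Table 4 and re-doses in line with it. The protocol never says that 11.1.2 overrides or supplements the table. Nor does anything show that the omission was deliberate: the infusion-reaction row carries a permanent stop for a Grade 2 event that develops despite premedication, so row-specific Grade 2 stops were within the table's scope.

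Two practical points also stand. This is a single-center trial whose team reviews each patient at least monthly (Section 7.4.1), so the risk is that the team overlooks 11.1.2 or that two clinicians read the protocol differently, not that sites diverge. That review may catch a case, but it does not say which rule governs.

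The 0.8% rate may also not transfer. Exclusion 2.1.2.9 removes patients with earlier steroid-treated pneumonitis or interstitial lung disease, and the protocol does not say whether the 1567 patients were screened the same way.

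**Conclusion.** The concern holds. For a second Grade 2 pneumonitis that resolves and tapers in time, the operative dosing table permits re-treatment and 11.1.2 forbids it, with no mandatory rule to reconcile them.

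The affected number is small: at most 0.03 to 0.13 expected patients in the whole trial. The chance of any affected patient is at most 2.5% to 12.0%, or 0.6% to 3.2% in the lower scenario. These figures rest on the 0.8% rate applying here and on assumed recurrence of 10% to 50%; the lower scenario also assumes the two 50% shares. The primary endpoint and the sample size are untouched. The change should be made because the possible harm is serious and the correction is very cheap, not because the event is likely.

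**What to change.** In Table 4, pneumonitis row, on the line that leads to permanent discontinuation, change the grade entry from '3-4' to '3-4, or recurrent Grade 2'. This uses the rule already in 11.1.2, and no other edit is needed.

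The cost is one phrase in one cell, with no change to sample size, visits or data collection. A patient with a resolved second Grade 2 episode would lose further treatment, as 11.1.2 already requires.

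### For a life-threatening hypophysitis or diabetes/hyperglycemia event, two Table 4 rows conflict with the Table 4 Note, and Sections 11.1.2 and 3.5.1 do not settle which applies

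*Combined protocol and SAP*

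**What the plan says.** **Table 4 Note (Section 3.3.1).** "Permanently discontinue for any severe or Grade 3 drug-related AE that recurs or any life-threatening event". No toxicity is exempted.

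**Table 4, hypophysitis row.** The hold column lists Grades 2 to 4 together. The restart column reads "Toxicity resolves to Grade 0-1. Therapy with pembrolizumab can be continued while endocrine replacement therapy is instituted". The discontinuation column covers only failure to resolve, or failure to reduce the corticosteroid, within 12 weeks.

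**Table 4, type 1 diabetes or hyperglycemia row.** The restart column holds the instruction "Hold pembrolizumab for new onset Type 1 diabetes mellitus or Grade 3-4 hyperglycemia associated with evidence of beta cell failure". The discontinuation column holds "Resume pembrolizumab when patients are clinically and metabolically stable".

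**Section 11.1.2.** The hypophysitis bullet says "Withhold pembrolizumab for Grade 2; withhold or discontinue for Grade 3 or 4 hypophysitis". The diabetes bullet says "Administer insulin for type 1 diabetes, and withhold pembrolizumab and administer anti-hyperglycemics in patients with severe hyperglycemia". A later bullet opens with "Other clinically important immune-mediated adverse reactions can occur" and ends with "Permanently discontinue pembrolizumab for any Grade 3 immune-mediated adverse reaction that recurs and for any life-threatening immune-mediated adverse reaction".

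**Section 3.5.1.** Removal from protocol therapy is required for treatment-attributed toxicity of Grade 3 or more that has not resolved to Grade 1 within 21 days of scheduled treatment. It is also required for autoimmune disease of Grade 3 or more that threatens vital organs. Neither criterion refers to Table 4.

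**The concern.** Section 4.1.3 sends the investigator to Section 3.3.1 for dose modification, so Table 4 is the working rule at the bedside. Its Note is absolute, while two of its rows offer only a path back to treatment, at grades that can include a life-threatening event. The case is foreseeable, because Section 4.1.3 counts diabetic ketoacidosis within the diabetes category. After such an event, whether a patient is re-dosed could depend on which line is read. Section 7.2.1 makes every protocol deviation reportable, so choices made under unclear precedence could later be called deviations. At stake are patient safety and consistent handling. The design's 4-of-15 response criterion is not affected by this point.

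**Working it through.** The main check is textual: the rules are set side by side for one case, an event judged life-threatening.

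| Source | Hypophysitis | New type 1 diabetes, or Grade 3-4 hyperglycemia with beta cell failure |
|---|---|---|
| Table 4 row | Hold; restart at Grade 0-1; no separate Grade 4 line | Hold; resume when stable; no discontinuation criterion |
| Table 4 Note | Stop permanently | Stop permanently |
| 11.1.2, event's own bullet | Withhold or discontinue at Grade 3 or 4 | Withhold in severe hyperglycemia |
| 11.1.2, bullet on other reactions | Stop permanently, if the sentence reaches beyond its bullet | Same |
| 3.5.1 | Remove if unresolved at 21 days, or if autoimmune disease of Grade 3 or more threatens vital organs | Same |

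**Step 1. Rows against Note.** Table 4 has ten rows. Seven (colitis, hepatic, hyperthyroidism, infusion reaction, pneumonitis, renal, all other) end in a line ordering permanent discontinuation at Grade 4 or Grades 3-4. Hypothyroidism has no hold grade. The two rows at issue are the only ones that hold at Grade 4 and have no such line. The hepatic row flags its exception explicitly; these two rows flag none. Rows and Note therefore conflict for a life-threatening event.

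**Step 2. Section 11.1.2.** The two event-specific bullets are compatible with the rows. The permanent-stop sentence agrees with the Note, but it stands in the bullet on other reactions. The section supports both sides and does not break the tie.

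**Step 3. Section 3.5.1.** For hypophysitis, Table 4 allows 12 weeks (84 days) from the last dose. If scheduled treatment in 3.5.1 means the next three-weekly dose, its limit falls at 21 + 21 = 42 days after the last dose. If it means the dose already given, the limit falls at 21 days. The two limits differ by 84 - 42 = 42 days or 84 - 21 = 63 days. The vital-organ criterion may also cover some of the same events.

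**Step 4. Wording of the rows.** In the hypophysitis cell, the permission to continue could apply during the hold or only after resolution. In the diabetes row, the hold text is in the restart column and the resume text in the discontinuation column.

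**Step 5. Expected frequency.** Inputs: Grade 4 hypophysitis 0.1% (Section 11.1.2) and 30 evaluable patients (Section 8). Assumption: the rate carries over to this population.

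- P(at least one) = 1 - (1 - 0.001)^30 = 0.030.
- A printed 0.1% could be anything from 0.05% to 0.15%: 1 - 0.9995^30 = 0.015 and 1 - 0.9985^30 = 0.044.
- For diabetes, the protocol gives 3 of 2117 for type 1 diabetes of any severity. That is not a rate of life-threatening events, so no matching figure can be computed.

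**The case against.** The strongest reply is that a workable reading exists. The hypophysitis row sets a condition for restart and permits continuation; it does not order re-dosing. An investigator who treats the Note as an override breaks nothing in that row. Only the diabetes row uses an imperative. The trial is single-center and the team discusses each patient at least monthly, so inconsistent handling is less likely than across many sites. This lowers the practical risk. It does not remove the conflict, because nothing says that the Note overrides the rows, and the two event-specific bullets in 11.1.2 could equally be read as confirming the rows as exceptions.

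Four stronger readings are tempting and are not supported:

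- **Every Grade 4 event triggers the Note.** Table 5 links Grade 4 to life-threatening for infusion reactions only. Section 7.1.7 defines life-threatening by immediate risk of death in the view of the investigator or sponsor, not by grade. A Grade 4 event not judged life-threatening falls under its row alone.
- **Section 11.1.2 requires a permanent stop for these events.** Its event-specific bullets do not.
- **Every Grade 2 to 4 hypophysitis is told both to hold and to continue.** The cell can be read in sequence: hold, restart at Grade 0-1, with replacement therapy no bar. It is ambiguous, not plainly contradictory.
- **All Grade 3-4 hyperglycemia is affected.** The row's hold instruction is limited to cases with evidence of beta cell failure.

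The misplaced diabetes text is partly a formatting matter, since its hold-then-resume meaning is clear. Even with the text moved back, the discontinuation column would be empty.

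**Conclusion.** This is an internal inconsistency that should be corrected. It is confined to events judged life-threatening in two Table 4 rows. For those, the rows and the Note conflict without stated precedence, 11.1.2 holds both positions, and 3.5.1 overlaps without alignment. The ambiguous hypophysitis cell and the missing diabetes discontinuation criterion are smaller drafting faults in the same rows.

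Frequency is low and severity high. The chance of at least one Grade 4 hypophysitis in 30 patients is about 3% (1.5% to 4.4% allowing for rounding of the printed rate). This rests on the pooled rate applying here, and it describes the conflict only so far as such events are judged life-threatening. The corresponding chance for diabetes or hyperglycemia is unknown from the documents. No effect on response follow-up has been shown.

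**What to change.** Reconcile the two Table 4 rows, the Table 4 Note, Section 11.1.2 and the removal criteria in Section 3.5.1 in one amendment:

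- State which rule takes precedence for a life-threatening event in these two rows. Either give such events their own line in each row, or have the Note say whether the rows are exceptions to it.
- Say whether the permanent-stop sentence in 11.1.2 applies beyond its own bullet.
- State how the 21-day and vital-organ criteria in 3.5.1 relate to the 12-week limit in Table 4.
- Make clear whether continuation in the hypophysitis cell applies during the hold or only after resolution, and for which grades.
- Put the diabetes row's hold and resume text in the matching columns, and state its discontinuation criterion or say that there is none.

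Which rule stands is the sponsor's clinical decision. The cost is text in one amendment; no procedure, visit or patient is added.
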